8.6 Data and Safety Monitoring Plan (DSMP)

An independent DSMB will be created to review the accruing data to: 1) ensure that study conduct, enrollment, and patient follow-up is adequate; 2) ensure that there are no serious safety concerns; and 3) assess evidence related to patient-reported QoL. The DSMB will be enlisted by the DCC in consultation with the executive committee.

The primary objective for interim analyses is to allow careful and continuing analysis of safety outcomes by randomization group. We will record and present all SAEs that occur during followup, but focus interim monitoring for those events that occur within the first four weeks of followup (since this is the time period in which the major treatment related events would be expected). The DSMB will review safety and efficacy data reports every six months and will conduct formal interim analyses for efficacy and safety once enrollment in the randomized cohort meets targets of 400 and 800-1000 participants. We anticipate these targets will align with analysis occurring at 18 and 30 months following enrollment. If recruitment in the study is slower than expected, the DSMB will be encouraged to consider as a contingency that investigators continue to recruit patients for up to 4.5 years with the goal of accomplishing the Aim 1 analysis (four-weeks) in all, acknowledging that longer term outcomes will only be assessed in a subset of patients. At sample sizes considerably smaller than that projected (Table 5), the study will have sufficient power to address Aim 1, excluding the non-inferiority margin when large differences in EQ-5D are observed (e.g., 3%).

[name] Study Protocol Version 6.1 February 2019

1. Safety Monitoring – We will perform interim analyses of accruing safety data. SAEs (described in section 9.1) will be monitored throughout the course of the study. The DSMB will review tabulated SAEs by treatment group every six months; however, all deaths will be reported to the DSMB immediately. With additional guidance from the DSMB, we propose to monitor and compare three safety endpoints between randomization groups: 1) per-patient indicator of "any" SAE, 2) per-patient SAE count, and 3) all-cause mortality. The research coordinators at each practice site will monitor participants for, or be alerted by UW study staff regarding the presence of, SAEs and AEs during inpatient stays using EMR. This process includes reviews of SAEs and AEs that occur at other hospitals not included in the study, with details obtained through requested records from those hospitalizations. An adjudication process related to these events will be led by a clinician not otherwise involved in the trial. This independent safety monitor (ISM) will review SAE forms for data quality control. SAE forms needing additional specification will be returned to the site PI for completion prior to finalization. All SAEs will also be adjudicated by the surgical site lead.

Based on data from prior studies, we anticipate that SAEs in the ITT antibiotics arm will be less common than in the appendectomy arm. Since appendectomy is considered standard of care and it is desirable to assess effectiveness within subgroups, we do not propose formal statistical stopping rules if SAE rates are lower in the antibiotics arm. However, evidence of higher SAEs in the antibiotics arm will require DSMB consideration of the trial's continuation. At the planned interim analysis, we will use onesided tests to formally compare the event rates across the two ITT treatment groups using appropriate small sample methods such as Fisher's exact test or Poisson regression with robust standard errors for SAE per-patient counts. We will also monitor and compare the rates of SAEs in the appendectomy arm to the rate of SAEs among patients in the observational cohort who receive appendectomy to address concerns that surgery following antibiotic therapy may be associated with a higher surgical risk. For safety monitoring we will utilize a one-sided Pocock stopping boundary^{38,39} (α =0.025) where, at the discretion of the DSMB and faculty statistician, study recruitment may be discontinued if there is substantial statistical evidence for a higher safety event rate in the antibiotics arm compared to the appendectomy arm (P<0.011 at either interim or final analysis). In other words, the DSMB will consider stopping the trial on the basis of safety if there is substantial statistical evidence that patients randomized to the antibiotics treatment are experiencing a higher rate of SAEs than patients randomized to appendectomy.

2. Efficacy Monitoring – The DSMB will monitor patient-reported EQ-5D scores at four-weeks using a sequential monitoring boundary for futility. Conditional power will be used to assess futility, the likelihood of the trial to show non-inferiority at the final analysis. This will be done by calculating the probability of demonstrating non-inferiority in the ITT analysis, conditional on the observed results and on assumptions about the future results of the trial. Using conditional power for sequential monitoring of efficacy data, the type II error rate (β) for the study is bounded by $\beta/(1-\epsilon)$, where ϵ denotes the conditional power monitoring threshold. At the recommendation of Bratton et al. (2012), the DSMB will consider stopping the trial for futility (based on EQ-5D) if conditional power falls below a fixed threshold of ϵ =0.10.40 In other words, the trial would only stop on the basis of the EQ-5D if the EQ-5D in the antibiotics arm is worse than that of patients randomized to appendectomy by a substantial margin. Futility analyses related to the EQ-5D will be balanced by the DSMB against the need to determine the rates of early

- antibiotic failure overall, and in *a priori* selected subgroups (e.g., older patients and Medicaid beneficiaries), as well as other important clinical endpoints.
- 3. Early Antibiotics Failures Monitoring In a non-inferiority study, treatment with appendectomy in the antibiotics arm may bias the study conclusions towards declaring non-inferiority of the antibiotics approach. In conjunction with safety and PROs, the DSMB will review the rate of eventual appendectomy in the antibiotics arm as a measure of adherence to protocol and study quality. No formal stopping rules are proposed on the basis of crossover or early antibiotics failure rates overall or within subgroups.
- 4. Subgroup Monitoring As an important clinical subgroup of interest, the DSMB will actively monitor patients with appendicolith on safety, PROs, and the rate of treatment by appendectomy among those randomized to receive antibiotics. No formal stopping rules are proposed based upon results observed within the appendicolith subgroup because patient advisors determined that information for this substantial group of patients would be informative to decision makers even if only a small proportion (<25%) had successful treatment with antibiotics. Another clinical subgroup of interest includes patients treated with different antibiotic types and/or regimens and specifically those who received completely outpatient versus at least some inpatient antibiotic therapy. The DSMB will actively monitor patients based on antibiotics received and whether or not they ultimately had surgery. Subgroup monitoring will focus on safety, PROs, and the rate of eventual appendectomy. No formal stopping rules are proposed based on results observed within the antibiotic type and regimen subgroups since patient advisors determined that information for this group of patients would be informative to decision makers.

- 5. Revisions These monitoring guidelines may be revised at the discretion and recommendation of the DSMB.
- 6. DSMB Recommendations After each interim review of the data, the DSMB will recommend one of the following actions:
 - a. Continuation of the study as is;
 - b. Continuation of the study with protocol changes in the interest of safety or study accrual;
 - c. Discontinue the study due to inadequate patient accrual, follow-up, or study conduct;
 - d. Discontinue the study due to patient safety in the antibiotics arm; and
 - e. Discontinue the study for futility, low conditional power for the primary question of interest.
- 6. Shell DSMB report tables are located in Appendix A.

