6.2 Secondary Outcomes

6.2.1 Clinical Complications

Death, SAEs, and complications (reported as AEs via EMR review) will be assessed and recorded through the study surveillance period. Complications (reported as AEs) will incorporate NSQIP standards and definitions as well as events related to antibiotic-related complications.

Serious Adverse Events	Adverse event
Death	
Life-threatening event	
Severe antibiotic reaction	Mild/moderate antibiotic reaction
CVA or stroke	
MI requiring treatment or cardiac arrest	Myocardial infarction Atrial arrhythmia
Unplanned admit to ICU	
Acute Renal Failure (requiring dialysis)	Major UTI (e.g., pyelonephritis) Urinary retention Acute Renal Failure (no dialysis) Progressive renal insufficiency
C. difficile colitis (requiring colon resection)	
Pulmonary embolism requiring therapy	DVT/PE requiring treatment
Coma >24 hours	
Septic shock (requiring pressors)	Sepsis
Serious Adverse Events (continued)	Adverse event (continued)
Bleeding requiring transfusion	
Newly infected prosthetic graft infection	
(such as a cardiac valve that gets infected or	
synthetic bypass graft infection secondary to	
appendicitis)	
Mechanical ventilation >48 hours	Tracheal reintubation/tracheostomy
Colostomy or ileostomy	NG tube replacement (non-routine)
	Bowel obstruction
	Ileus
	Organ/space infection (including peritonitis)
	Surgical site infection
	Intra-ab Abscess
	Severe dehydration
	Hernia
	Malignant hyperthermia
	Pneumonia
	Other infection
	Other post-op occurrence: unspecified
	Other non-operative intervention: unspecified
	Unplanned (re)operative intervention during index
Other life threatening count	C. difficile colitis (not requiring colon resect)
Other life threatening event	
Rehospitalization (other than for txt of appendicitis)	

Monitored event
Appendiceal cancer
Perforation
Length of stay postoperatively

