12.0 Protection of Human Participants

We expect that most patients will have good baseline health but will not exclude patients with most stable and chronic medical conditions, other than those with complicated appendicitis and characteristics described in exclusion criteria.

Because the proposed study population will include Spanish-speaking patients, all consent documents and materials will be translated to Spanish. Women of childbearing potential will be excluded if they have a positive pregnancy test documented prior to enrollment or anticipate being pregnant in the following month. Prisoners will be excluded. There is no evidence from prior studies to suggest there will be differences in intervention effect among sex/gender or racial/ethnic subgroups.

The risks and benefits for participants enrolled in this trial are appropriately balanced. Both of the study interventions (appendectomy and IV antibiotics) are standard, and all of the drugs used in the study are currently in clinical use. Potential risks to participants include the potential AEs that are well described as complications of acute appendicitis, including appendiceal perforation, intraabdominal abscess, sepsis, pain, and loss of time from work and normal activities. Based on prior studies, it is not expected that these complications will be greater in patients assigned to the non-operative strategy group, but that is not known for certain. Patients assigned to the operative strategy will be participant to the well-described risks of surgery including adverse anesthesia reaction, perforation of viscus, wound infection, or bleeding. These risks would be similar to those that patients with AUA would encounter as part of standard care. All patients will also have potential risks of adverse reaction to antibiotics including allergic reaction or antibiotic-associated and Clostridium difficile colitis. Other risks include potential loss of patient confidentiality through the collection of study data. It is expected that the benefits of the study (including avoidance of surgery and its associated risks in the nonoperative group and the benefits of the knowledge gained that will improve patient choices in the future) justify the potential risks.

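### The interim safety trigger tests only SAEs and deaths, so an excess of abscess, peritonitis or sepsis without pressors reaches it only through cases that also meet an SAE criterion, and the readmission exemption is worded in two ways

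*Protocol*

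**What the plan says.** Protocol section 8.6, item 1, sets out what will be tested: "three safety endpoints between randomization groups: 1) per-patient indicator of 'any' SAE, 2) per-patient SAE count, and 3) all-cause mortality". It continues: "For safety monitoring we will utilize a one-sided Pocock stopping boundary", with one-sided alpha 0.025. The DSMB and the faculty statistician may discontinue recruitment when "there is substantial statistical evidence for a higher safety event rate in the antibiotics arm compared to the appendectomy arm". The nominal level for that evidence is given as "P<0.011 at either interim or final analysis". The next sentence restates the trigger as a higher rate of SAEs on antibiotics. Formal looks are set at 400 and at 800 to 1000 randomized, and interim monitoring concentrates on the first four weeks.

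The table in section 6.2.1 decides what counts as an SAE. Intra-abdominal abscess, organ/space infection including peritonitis, and sepsis are in the adverse-event column. Sepsis moves to the SAE column only as septic shock needing pressors. Perforation is in a third list of monitored events. The SAE column also holds life-threatening events, unplanned ICU admission and "Rehospitalization (other than for txt of appendicitis". Section 9.2 gives a second SAE definition, in which inpatient hospitalization counts unless it is for treatment of recurrent appendicitis.

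Section 12.0 lists the potential risks to participants as "appendiceal perforation, intraabdominal abscess, sepsis, pain, and loss of time from work and normal activities".

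**The concern.** The boundary exists to warn the DSMB if patients assigned to antibiotics are being harmed. Abscess and sepsis are harms the protocol itself names, yet neither they nor peritonitis is compared between arms at the interim looks in its own right. A case that arises and is managed in the index stay, or as an outpatient, adds nothing to any tested endpoint unless it meets some other SAE criterion. A substantial excess could therefore build up while the DSMB is correctly told that no boundary has been crossed.

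The readmission route adds an ambiguity. Consider a patient with the appendix in place who is readmitted at two weeks with an abscess. Under the 6.2.1 wording this could be read as treatment of appendicitis and left out. Under the 9.2 wording it could count, because the index episode is not a recurrence. After appendectomy the exemption is harder to invoke, so the ambiguity may fall unevenly on the arms.

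**Working it through.** **1. The plan's own threshold.** Inputs from sections 8.5 and 8.6: one-sided alpha 0.025, interim looks at 400 and 800 to 1000, final N 1552. A Pocock boundary solves Pr(any Z_k > c) = 0.025, with corr(Z_i, Z_j) = √(n_i/n_j) for n_i < n_j.
- Three equally spaced looks: c = 2.2895, nominal P = 0.01103, which matches the stated 0.011.
- Two looks: nominal P = 0.01469, no match. The stated figure therefore implies three looks.
- Looks at 400, 800 to 1000 and 1552: nominal P = 0.0105 to 0.0106. Using 0.011 spends 0.0259 to 0.0263 per endpoint, a trivial excess.

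The threshold is sound. The issue is what is fed into it.

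**2. How much of an excess reaches the any-SAE endpoint.** The documents give no event rates, so everything here is assumed:
- b = 3%, background SAE rate in both arms;
- h = per-patient rate of abscess, peritonitis or sepsis, 3% after appendectomy and 6% or 9% on antibiotics;
- f = share of those cases that also meet an SAE criterion.

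Any-SAE rate in an arm = 1 − (1 − b)(1 − f·h). With f = 0.5 and h = 3% v 9%:
- appendectomy: 1 − 0.97 × 0.985 = 4.46%
- antibiotics: 1 − 0.97 × 0.955 = 7.37%

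A threefold difference in the harm becomes a ratio of about 1.65 in the tested endpoint.

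**3. Probability of crossing.** One-sided Fisher exact test, P<0.011, looks at 200, 450 and 776 per arm (450 is the midpoint of the second target), calculated exactly from the binomial distributions. Cells show crossing by the second look / by the final look.

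| Endpoint tested | 3% v 6% | 3% v 9% |
|---|---|---|
| Any SAE, f = 0 | 1.1% / 1.7% | 1.1% / 1.7% |
| Any SAE, f = 0.25 | 3.9% / 6.8% | 9.8% / 19% |
| Any SAE, f = 0.5 | 8.6% / 17% | 30% / 56% |
| Any SAE, f = 0.75 | 16% / 31% | 56% / 84% |
| Any SAE, f = 1 | 25% / 47% | 77% / 96% |
| Composite tested directly | 42% / 71% | 93% / 99.7% |

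The f = 0 row is the false-alarm level. Even at f = 1 the any-SAE endpoint does worse than the composite, because background SAEs dilute the difference.

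**4. If the exemption bites unevenly.** Suppose half the cases qualify after appendectomy but only a quarter on antibiotics. With 3% v 9%, the any-SAE rates are 4.46% and 1 − 0.97 × 0.9775 = 5.18%. The trigger is crossed in 6.2% of trials over three looks, against 56% with even counting. This shows what unequal coding would do. The documents do not show that it would occur.

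**5. Cost of a fourth endpoint.** With equal composite rates of 1%, 2%, 3% and 4% in both arms, the composite crosses over three looks in 1.0%, 1.4%, 1.7% and 1.7% of trials.

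**The case against.** The strongest reply is that an SAE-based, discretionary boundary is a legitimate choice and the board is not confined to it. The three endpoints are offered subject to DSMB guidance, and section 8.6 lets the DSMB revise the monitoring guidelines. It also sees safety reports every six months. The shell tables in Appendix A are not in the available text, so by-arm tabulation of these events may already be planned. Complications are compared by arm under Aim 2. All of this stands. However, Aim 2 is an outcome analysis rather than a safety trigger, and the by-arm tabulation that section 8.6, item 1, specifies is of SAEs only.

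A reader might infer that an excess of these harms cannot trip the rule at all. The documents do not support that. A patient who is readmitted on non-exempt grounds, goes to the ICU unplanned, needs pressors or has a treatment-related life-threatening event has an SAE and is counted.

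A reader might also infer that the exemption systematically hides harm on antibiotics. That is not documented either. Section 9.2 exempts only recurrent appendicitis, and section 4.5.2 discusses recurrence for returns after the four-week assessment, whereas interim monitoring concentrates on the first four weeks. Records are abstracted to settle whether recurrence was confirmed (section 6.2.2), and SAEs are adjudicated. What is documented is that the two wordings differ.

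Finally, section 12.0 presents these events as complications of appendicitis that any participant may suffer, and does not expect more of them without surgery. They are not described as specific to antibiotics. The one-sided boundary is there to check that expectation.

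**Conclusion.** The point holds as a gap in coverage and an inconsistency in wording. No formal interim comparison covers abscess, organ/space infection including peritonitis, or sepsis without pressors. An excess reaches the trigger only through the cases that also qualify as SAEs. For an assumed tripling of these harms, detection over three looks falls from nearly certain with a direct comparison to about 56% if half the cases qualify and to the false-alarm level if none do. For a doubling, the corresponding figures are 71%, 17% and under 2%.

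These sizes rest on assumed event rates, an assumed background SAE rate and an assumed qualifying share. The direction does not depend on the particular values. Uneven capture between the arms is a plausible inference from the conflicting exemptions, not something the documents establish. The change is worthwhile because it is cheap and improves safety detection. It does not imply that the existing rule is invalid.

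**What to change.** 1. Reconcile the readmission exemptions in sections 6.2.1 and 9.2 into one definition, so that the same kinds of readmission count as SAEs in both arms. At the same time, correct the pointer in section 8.6, item 1, which refers to section 9.1 for the SAE description although the definition is in section 9.2.
2. In section 8.6, item 1, add a fourth by-arm comparison: a per-patient indicator of intra-abdominal abscess, organ/space infection or peritonitis, or sepsis arising after randomization. Count it identically in both arms, whether or not the patient was readmitted. Exclude findings already present at the index operation, since they would otherwise be seen mainly in the appendectomy arm, and list them separately with perforation.
3. Test it one-sided by Fisher's exact test at the existing looks, with P<0.011 as a prompt for DSMB discussion, and tabulate it by arm in the six-monthly report. If the Appendix A shells already tabulate these events by arm, only the definition and the formal comparison need adding.

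The cost is protocol and report wording and one more table, from adverse-event data already abstracted at record review. The composite becomes a fourth endpoint with no multiplicity control, adding about 1.0% to 1.7% false alerts over three looks if its rate is 1% to 4%. An alert leads only to DSMB discussion. Nothing in treatment or clinical management changes.

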8.5 Sample Size and Statistical Power

Prior studies suggest that non-clinical outcomes (e.g., loss of time from work and pain scores) were similar between groups, but did not evaluate a global QoL measure. The EQ-5D QoL

index ranges from 0 (worst QoL) to 1 (highest QoL), where anchor-based methods have shown that the MCID ranges 5%-10%. Based on data from a prior study of appendectomy with EQ-5D scores at 12 weeks, we estimate that the mean EQ-5D for appendectomy patients will be 0.90 with a standard deviation of 0.12. In order to assess QoL differences between interventions, we will recruit a total of 1552 patients assuming a 90% follow-up at four-weeks. This gives the study high power (>99%) to rule out EQ-5D differences between-groups as small as 5% (e.g., if we observe treatment differences of 0 to 2%) and 80% power if we observe a treatment difference of 3% (Table 5, below).

Previous Washington State evaluations of patients undergoing appendectomy (Table 1). identified that 2-3% of the population is African American, 10-12% Hispanic, 10-15% are Medicaid beneficiaries, and 10% will be above 64 years of age. Recruiting 1552 total patients will allow for a subgroup evaluation based on older age and Medicaid beneficiary status. Assuming 50% recruitment of these populations we anticipate including ~500 Medicaid beneficiaries and ~450 patients ≥65 years. As demonstrated in Table 5, this study also has adequate power (>80%) to rule out differences of 5% for observed treatment effect of Δ =0% within subgroups as small as n=250 patients, or treatment differences of Δ =-1% within subgroups of at least n=400. For this reason, we expect the study will be able to assess these two subgroups. All other subgroup evaluations will be post hoc and used for hypothesis development only.

Table 5. Statistical Power to Declare Non-inferiority on Patient-reported QoL, Overall and by

Subgroup (Non-inferiority Margin, M = -5%, one-sided α =0.025).

Treatment Difference A	Overall		Subgroups	
Treatment Difference, Δ	N=1552	N=250	N=400	N=500
-3%	82.6%	-	-	-
-2%	99.4%	-	57.1%	67.9%
-1%	100%	62.4%	83.8%	91.4%
0%	100%	83.0%	96.4%	98.8%

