9.2 SAE Reporting

Life-threatening complications or SAEs are a very rare possibility with surgical treatment and even less likely with antibiotic treatment. SAEs are defined as one of the following conditions (also listed in section 6.2.1):

- 1. Death during the period of protocol-defined surveillance;
- 2. Life-threatening event related to the treatment or significant disability/incapacity related to the treatment; or
- 3. Inpatient hospitalization (other than for treatment of recurrent appendicitis).

All SAEs will be:

- 1. Recorded on the appropriate SAE case report form;
- 2. Adjudicated by the ISM;
- 3. Reviewed and evaluated by the DSMB;
- 4. Followed until satisfactory resolution or until the study investigators deem the event to be chronic or the participant to be stable;
- 5. Reported to the study investigators, the project managers, and site IRBs per their reporting guidelines; and
- 6. The study investigators will also report SAEs to PCORI in its role as funder.

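### The robust-SE Poisson test named for per-patient SAE counts breaks down when the appendectomy arm has no SAEs: one antibiotics-arm event then crosses P<0.011

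*Protocol*

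**What the plan says.** Protocol section 8.6, item 1, compares three safety endpoints between the randomized arms: whether a patient had any SAE, the number of SAEs per patient, and all-cause mortality. On sidedness and population it says: "we will use onesided tests to formally compare the event rates across the two ITT treatment groups". Two methods are then offered as suited to small samples. One is Fisher's test, which fits the two binary endpoints. The other is "Poisson regression with robust standard errors for SAE per-patient counts", the only method named for the count.

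The results are judged against a "one-sided Pocock stopping boundary" with overall α = 0.025, stated as "P<0.011 at either interim or final analysis". The formal interim looks come "once enrollment in the randomized cohort meets targets of 400 and 800-1000 participants", and section 8.5 plans to "recruit a total of 1552 patients". Interim monitoring concentrates on events in the first four weeks. Section 9.2 says that "SAEs are a very rare possibility with surgical treatment and even less likely with antibiotic treatment" and gives no rate.

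The protocol does not say which test statistic the Poisson model should supply, or what to do if an arm has no events. The final SAP has no section on interim safety testing.

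**The concern.** A stopping boundary controls error only if the p-values fed into it are valid at the event counts expected. At the first look there are about 200 patients per arm, four weeks of events are the focus, and the protocol itself expects SAEs to be very rare. An appendectomy arm with no SAEs is then a foreseeable table.

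That is where a robust-SE Poisson fit fails. The estimated log rate ratio runs off to infinity while the sandwich standard error stays near 1, so the Wald p-value goes to zero whatever the evidence. At stake is a spurious safety signal against antibiotics, and the claim that this endpoint is monitored at a one-sided 0.025.

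**Working it through.** **1. The plan's threshold.** Two interims and a final analysis make three looks. The Pocock constant c solves P(any Z_k > c) = 0.025 with corr(Z_j, Z_k) = √(t_j/t_k). Three equally spaced looks give c = 2.2895 and 1 − Φ(c) = 0.01103, which is the stated 0.011. Spacing of 400/800/1552 gives 0.01045 and 400/1000/1552 gives 0.01059. The threshold is not in question.

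**2. The Wald statistic.** Let a of n antibiotics patients and b of n appendectomy patients have one SAE each. The log rate ratio is ln(a/b). Each arm adds Σ(y − μ)²/(nμ)² to the sandwich variance. For an arm with a events this is (1/a)(1 − a/n).

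- For an empty arm, y = 0 and the fitted μ tends to 0. The contribution is nμ²/(nμ)² = 1/n, which is 0.005 at n = 200 (software may return about 0).
- For a = 1, b = 0, n = 200, the antibiotics arm adds 1 − 1/200 = 0.995. The SE is therefore between √0.995 = 0.9975 and √(0.995 + 0.005) = 1.
- The log rate ratio has no finite value, and software stops wherever its tolerance allows. At a tolerance of 1e-8 it stops at 20.39, so z = 20.39/0.9975 = 20.4 and p is 0 to machine precision.
- Over tolerances from 1e-2 to 1e-10, iteration caps from 3 to 25 and two other optimizers, the largest p was 7e-13.
- The model-based SE for the same fit is 16,210, giving p = 0.499.

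**3. Comparators at 200 per arm.** Fisher for 1 v 0 is 200/400 = 0.50. For 3 v 0 it is (200·199·198)/(400·399·398) = 0.124, against a robust z of 37. Fisher first crosses 0.011 at 7 v 0. A robust score test for 1 v 0 gives p = 0.158.

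**4. How often it happens.** The SAE rate p is an assumption, shown as a range. The arms are taken as equal, with at most one SAE per patient. With an empty appendectomy arm every a ≥ 1 crosses, so with q = (1 − p)^n the chance is q(1 − q), plus a small part from tables with b ≥ 1 found by enumeration. The q(1 − q) part cannot exceed 0.25.

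| Rate p | q, n = 200 | q(1 − q) | Total, robust Wald | Fisher |
|---|---|---|---|---|
| 0.5% | 0.3670 | 0.2323 | 23.2% | <0.01% |
| 1% | 0.1340 | 0.1160 | 11.6% | 0.06% |
| 1.5% | 0.0487 | 0.0463 | 4.6% | 0.22% |
| 2% | 0.0176 | 0.0173 | 1.8% | 0.38% |
| 3% | 0.0023 | 0.0023 | 0.45% | 0.56% |

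The second look falls at 400 to 500 per arm. At 450 per arm and p = 0.5%, q = 0.995^450 = 0.1048, and 0.1048 × 0.8952 = 9.4%. At p = 1%, q = 0.0109 and the total is about 1.15%.

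**5. When the appendectomy arm is not empty.** For 9 v 1 at n = 200, the variance is (1/9)(1 − 9/200) + (1 − 1/200) = 0.1061 + 0.9950 = 1.1011. The SE is 1.0493, z = ln 9/1.0493 = 2.09, and p = 0.018, so the count test does not cross. Fisher on the same patients gives p = 0.00998, which does.

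**The case against.** The wording is permissive. The two methods are introduced as examples, the governing word is appropriate, and no Wald test is prescribed. A robust score test is also a robust Poisson analysis and does not collapse. This stands as a limit: the failure belongs to the Wald test. But Wald is what a robust-SE Poisson fit ordinarily reports, and nothing in the plan steers the analyst elsewhere.

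The SAE rate may not be low. Section 9.2 counts inpatient hospitalization other than for recurrent appendicitis as an SAE, and at 3% the problem is gone. Section 8.6 also expects more SAEs on appendectomy, which makes an empty appendectomy arm less likely. At an assumed 1% on antibiotics and 2% on appendectomy, the chance of zero on appendectomy with at least one on antibiotics is 0.0176 × (1 − 0.1340) = 1.5%. This also stands, and it is why the size is given as a range.

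Three stronger readings are tempting, and the documents do not support them.

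- *A single SAE could halt the trial.* Crossing leads to consideration at the discretion of the DSMB and the faculty statistician. They see SAEs tabulated by arm and would probably recognise a 1 v 0 signal as an artefact.
- *The boundary would miss a real excess such as 9 v 1.* The any-SAE endpoint is monitored too, and Fisher's test on it crosses there.
- *The 0.025 level fails whatever the SAE rate.* It fails only at low rates.

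Discretion lessens the consequence but does not repair the test. A boundary that has to be overruled whenever one arm is empty does not hold its stated error rate.

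**Conclusion.** The point holds in a limited form. Robust-SE Poisson regression with a Wald test is not a small-sample method, and with no appendectomy SAEs it turns one antibiotics SAE into a crossing. Under equal rates and at most one SAE per patient, the first look alone exceeds the whole 0.025 allowance at the assumed rates of 0.5% to 1.5% (4.6% at 1.5%). It exceeds the nominal 1.1% at 2% and is below it at 3%. At the second look the excess has nearly gone by a rate of 1%.

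The defect is confined to one of three advisory safety endpoints. It does not touch the Fisher tests on any SAE and mortality, or the EQ-5D analysis. Severity is minor to moderate. The main uncertainty is the SAE rate, which the documents leave unstated.

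**What to change.** In protocol section 8.6, item 1, replace robust-SE Poisson regression for the per-patient SAE count with a one-sided permutation test of the mean count by randomized arm, at the same 0.011. It is valid with an empty arm (1 v 0 gives 0.50), allows repeat events in a patient, and reduces to Fisher's test when no patient has more than one SAE. A robust score test would also avoid the zero-cell failure.

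Keep Fisher's exact test for any SAE and mortality. Report the Poisson rate ratio only as a description, and only when both arms have events.

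The cost is one sentence and a few lines of code. Patients, looks and threshold do not change, and item 5 of section 8.6 already lets the monitoring guidelines be revised on the DSMB's recommendation.
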